## Cover Page for Study Protocol

Sponsor name	Sesen Bio, Inc.*
NCT Number	NCT02449239
Sponsor trial ID:	VB4-845-02-IIIA
Official title of study	Open-Label, Multicenter, Ph 3 [Phase 3] Study to Evaluate the Efficacy and Tolerability of Intravesical Vicinium™ in Subjects With Non Muscle-Invasive Carcinoma in Situ and/or High-Grade Papillary Disease of the Bladder Treated With BCG
Document Date	26 January 2017

\*Note: Sponsor subsequently underwent a name change (from Eleven Biotherapeutics, Inc. to Sesen Bio, Inc.) but the protocol was not amended with the new Sponsor name

Version Number	Summary of Changes
4.0	
 
• Updated Sponsor name from Viventia Bio, Inc. to Eleven Biotherapeutics, Inc.
 
• Updated exploratory endpoints - added inclusion of biomarker status from positive bladder biopsies, added provision for additional PK sampling in the event of renal or hepatic AEs
 
• Added additional clarification on timing for prior adequate BCG status
 
• Exclusion criteria modified to include: subjects with T1 disease may have CT urogram or MRI urogram with or without (if indicated) contrast, subjects with UTI requiring antibiotic may defer treatment start until resolution of UTI, added allowance for patients with low-risk prostate cancer
 
• Hematology/Chemistry added requirement for chemistry labs during induction phase: drawn one day prior to dosing and results reviewed prior to dosing for weeks 1-6 and drawn within 3 days of last dose and within 4 days of current week's dose and reviewed prior to dosing for weeks 7-12; added requirement to draw chemistry labs within 5 days of dosing and to review the results prior to dosing during maintenance phase
 
• Added Vicinium holding criteria for serum creatinine, creatinine clearance, AST, ALT levels, clinically significant UTI requiring antibiotics
 
• Added clarification regarding the adverse event handling of pre-existing medical conditions
 
• Added request for additional biopsy slides for potential evaluation of additional biomarkers
 

Version Number	Summary of Changes
3.0	
 
• Revised the patient population to include three cohorts and modified the primary and secondary endpoints to reflect this revision
 
• Added week 12 assessment of anti-Vicinium antibodies and modified the maintenance anti-Vicinium antibody target collection to a window encompassing weeks 23-27
 
• Added second restaging biopsy for subjects with T1 and clarified the requirements
 
• Specified that only most recent biopsy needs to occur within 8-week screening window
 
• Modified definition of women of childbearing potential and added requirements for contraception use
 
• Added inclusion criterion of Karnofsky performance status <math>\geq 60</math> and removed life expectancy of at least 4 years
 
• Clarified prior BCG to accurately define adequate BCG
 
• Revised QTc cutoff of <math>>470</math> to apply to all subjects and added details on conduct of assessments and allowances for known or suspected causes of QTc prolongation.
 
• Modified the inclusion criteria limits for creatinine and creatinine clearance
 
• Changed overall timing for study from months-based to weeks-based
 
• Changed Inclusion Criterion 2 timing of recurrence from 6 months to 26 weeks <math>\pm 2</math> weeks
 
• Changed timing for upper tract radiological imaging from 6 months to 26 weeks
 
• Added clarification on requirement for random biopsies
 
• Added information for a consent form for potential subjects to have their biopsy samples sent for central pathology review prior to signing the full study ICF
 
• Changed prostatic urethral biopsy from required to recommended for all male subjects with CIS.
 
• Changed timing wherein upper tract radiological imaging is required from within 6 months before start of dosing to within 13 weeks before start of dosing.
 
• Increased chemistry lab testing to weekly in the Induction Phase and every-other-week in the Maintenance Phase
 
• Changed physical examination from every 6 months to a targeted physical examination every 4 weeks
 
• Updated timing for post-treatment evaluations from within 2 weeks to 30-37 days after last dose
 
• Minor edits, typos and formatting corrections for consistency and clarity
 

Version Number	Summary of Changes
2.0	
 
• Removed presence of upper tract disease in the absence of disease in the urinary bladder as part of the complete response definition
 
• Added Event-free survival as a secondary endpoint and minor formatting of the Safety and tolerability of Vicinium therapy endpoint
 
• Specified inclusion of subjects with any grade T1 disease
 
• Removed the requirement for biopsy (directed and random) upon completion of the induction phase and at the 12-month time point during Maintenance
 
• Removed random biopsy as a requirement when not indicated
 
• Added that bladder biopsy must confirm diagnosis within 8 weeks of initiating study drug
 
• Added that bladder biopsy must confirm diagnosis within 8 weeks of initiating study drug
 
• Added evidence of higher stage disease by pelvic imaging to exclusion criteria
 
• Complete response rate updated to only include subjects with CIS with or without papillary disease
 
• Removal of prespecified efficacy threshold and update of censoring and event rules of EFS
 
• Removed presence of upper tract disease in the absence of disease in the urinary bladder as part of the complete response definition
 
• Clarified the definitions for treatment failure with respect to low-grade Ta and low-grade T1 recurrence
 
• Added the requirement for Complete Blood Count prior to the second of the twice weekly doses during weeks 2-6 of induction, pre-dose during weeks 7-12 of induction, and monthly during maintenance dosing
 
• Removed Month 12 (Primary Endpoint Evaluation)
 
• Added requirement for subject to be in the supine position when vital signs are measured
 
• The statement defining success as an exclusion of a 20% complete response rate by the lower limit confidence interval at 18 months was removed.
 

## 4 LIST OF ABBREVIATIONS

**Table 2: Abbreviations**

Abbreviation	Explanation
AE	adverse event
ALT	alanine transaminase
AST	aspartate transaminase
BCG	bacillus Calmette-Guérin
BIW	twice weekly
BUN	blood urea nitrogen
CBC	complete blood count
CI	confidence interval
CIS	carcinoma in situ
CRF	case report form
CTCAE	Common Terminology Criteria for Adverse Events
DoR	duration of response
DSMB	data safety monitoring board
ECG	electrocardiogram
EOS	end-of-study
EpCAM	epithelial cell adhesion molecule
ETA	exotoxin A
FDA	Food and Drug Administration
GCP	Good Clinical Practice
HIPAA	Health Insurance Portability and Accountability Act
IB	investigator's brochure
ICF	informed consent form
ICH	International Conference on Harmonization
IEC	Independent Ethics Committee
IND	investigational new drug application
IRB	Institutional Review Board
MedDRA	Medical Dictionary for Regulatory Activities
mg	milligram
mITT	modified intent-to-treat
mL	milliliter
msec	milliseconds
NCI	National Cancer Institute
NMIBC	non-muscle invasive bladder cancer
OS	overall survival
PFS	progression-free survival

Abbreviation	Explanation
QTc	corrected QT interval
RBC	red blood cell
SAE	serious adverse event
SD	standard deviation
SOC	system organ class
Ta	non-invasive papillary carcinoma
Tis	carcinoma in situ
T1	tumor invades lamina propria
T2	tumor invades muscularis propria
TCC	transitional cell carcinoma
TEAE	treatment-emergent adverse event
TPP	time to progression
TURBT	transurethral resection of bladder tumor(s)
ULN	upper limit of normal
UTI	urinary tract infection
WBC	white blood cell

## 6 SYNOPSIS

Name of Sponsor/Company: Eleven Biotherapeutics, Inc.	
Name of Investigational Product: Vicinium™	
Name of Active Ingredient: Oportuzumab monatox	
Title of Study: An Open-Label, Multicenter, Phase 3 Study to Evaluate the Efficacy and Tolerability of Intravesical Vicinium™ in Subjects with Non Muscle-Invasive Carcinoma in Situ (CIS) and/or High-Grade Papillary Disease of the Bladder Previously Treated with Bacillus Calmette-Guérin (BCG)	
Study center(s): Approximately 75	
Study period: Estimated date first subject enrolled: August 2015 Estimated date last subject completed: August 2018	Phase of development: 3
Objective(s): To assess the efficacy and tolerability of Vicinium when administered as a monotherapy intravesical instillation in subjects with non muscle-invasive bladder cancer - CIS, high-grade Ta or any grade T1 papillary disease or CIS plus papillary disease - who failed previous treatment (i.e., not those who are intolerant) with BCG.	
Endpoints: Primary: Complete response rate in subjects with CIS (with or without papillary disease) whose disease is refractory or relapsed in 6 months or less following adequate BCG treatment Duration of response (DoR) will be estimated (Kaplan-Meier Estimate) for those subjects with CIS (with or without papillary disease) who experience a complete response. Secondary: 

• Complete response rate and DoR in subjects with CIS (with or without papillary disease) whose disease is refractory or relapsed from 6 months to 11 months following adequate BCG treatment

• Complete response rate and DoR in all subjects with CIS (with or without papillary disease) following adequate BCG treatment

• Event-free survival (EFS) in all subjects

• Complete response rate in subjects at 3, 6, 9, 12, 15, 18, 21, and 24 months in subjects with CIS

• Time to cystectomy in all subjects

• Time to disease recurrence in all subjects

• Progression-free survival (PFS) in all subjects

• Overall survival (OS) in all subjects

• Safety and tolerability of Vicinium therapy in all subjects

 Exploratory: To evaluate biomarkers that may be associated with response or disease progression or treatment failure, which may include, for example, EpCAM status, tumor subtype morphology, furin levels in tumor cell endosomes, presence of a glycosaminoglycan coat, and presence of receptors that could impede a host anti-tumor immune response such as PD-L1.	

**Methodology:** This is an open-label, non-randomized, multicenter study in approximately 134 adults with non-muscle invasive bladder cancer (NMIBC). All subjects must have received “adequate BCG treatment” defined as at least 2 courses of full dose BCG, i.e., at least one induction course of at least 5 doses given within 7 weeks, and a second course (maintenance or second induction) of at least 2 doses given within 6 weeks. Full-dose BCG is:

- TICE® BCG: one vial of TICE containing 1 to  $8 \times 10^8$  colony-forming units (CFU) equivalent to approximately 50 mg (wet weight)
- ImmuCyst® BCG: one vial of ImmuCyst containing 81 mg (dry weight) equivalent to approximately  $10.5 \pm 8.7 \times 10^8$  CFU

or equivalent.

The “5+2” doses must be given within approximately 1 year (i.e., the start of one course to start of the second course within 12 months  $\pm 1$  month) and given to treat the same disease episode with which the subject is enrolling. Additional doses and courses of BCG are permitted as part of “adequate BCG.” All subjects must have disease for which the investigator would not treat with additional BCG treatment at this time.

Three cohorts of subjects will enroll:

- Cohort 1: Subjects with CIS with or without associated papillary disease whose disease is determined to be refractory or relapsed within 6 months of the last dose of adequate BCG treatment.
- Cohort 2: Subjects with CIS with or without associated papillary disease whose disease is determined to be refractory or relapsed more than 6 months but within 11 months of the last dose of adequate BCG treatment.
- Cohort 3: Subjects with high-grade Ta or any grade T1 papillary disease (without CIS) whose disease is determined to be refractory or relapsed within 6 months of the last dose of adequate BCG treatment.

For eligibility and cohort assignment, 6 months is defined as 30 weeks, i.e., 26 weeks (6 months) plus an additional 4 weeks to accommodate scheduling variations and for diagnostic work-up, and 11 months is defined as 50 weeks, i.e., 48 weeks (11 months) plus an additional 2 weeks to accommodate scheduling variations and for diagnostic work-up.

Of the 134 subjects  $\geq 77$  subjects will accrue to Cohort 1. Up to 57 additional subjects in total may accrue to Cohorts 2 and 3. This is an outpatient study. All treatments may be administered in the study clinic. Each subject’s study course consists of a Screening Period, a 12-week Induction Phase, a Maintenance Phase and a Post-Treatment Evaluation. Following the 12-week Induction Phase, subjects will be evaluated for disease status as described in **Section 14**. Subjects without a treatment failure as specifically defined in **Section 14.2** or other criteria necessitating discontinuation of study treatment (see **Section 11.3**) will begin the Maintenance Phase. Subjects will receive treatment for up to 2 years in total if they are tolerating treatment and do not meet the definition of protocol-defined treatment failure or other criteria for study discontinuation. Following the Post-Treatment Evaluation, additional subject data will be collected as needed for the evaluation of the Secondary Endpoints.

The treatments are as follows:

Induction Phase (Weeks 1-12)	30 mg of Vicinium in 50 mL of saline administered intravesically twice weekly (BIW) for 6 weeks followed by once weekly for 6 weeks, for a total of 12 weeks. The twice-weekly doses are to be administered at least 48 hours apart (and no more than 2 doses may be administered within a calendar week, i.e., within a Sunday through Saturday period.) As an example, while a Monday/Thursday or Tuesday/Friday would be optimal, a Monday/Wednesday, Tuesday/Thursday or Wednesday/Friday dosing schedule could be used. There will be a total of 18 doses over the 12-week period of the Induction Phase.
Maintenance Phase (up to Week 104)	30 mg of Vicinium in 50 mL of saline administered intravesically once every other week.

Screening/Baseline: Informed consent, indicated by the subject signing the ICF, must be obtained before any screening assessments or procedures are performed that are solely for determining study eligibility. Assessments and procedures performed as routine care or standard of care before the subject signs the ICF may be utilized to determine eligibility if these are performed within the study-specified time intervals. Screening procedures will include medical history, cystoscopy, urine cytology, directed biopsy, physical examination, 12-lead electrocardiogram (ECG), vital signs, and clinical laboratory analyses. Also, all female subjects of childbearing potential will take a urine or serum pregnancy test. Screening procedures are to be completed within the 8 weeks prior to the initial dose of study drug.
	

Drug Administration: Subjects will be asked to refrain from fluid intake 2 hours prior to and during the 2-hour period that study drug is held in the bladder to reduce urine flow during the instillation and dwell of Vicinium.
	

Immediately prior to bladder catheter insertion, subjects will empty their bladder. Appropriate study personnel will then insert a bladder catheter, and the bladder will be drained.
	

Vicinium 30 mg in 50 mL of saline will be administered intravesically through the catheter. After complete administration of the Vicinium dose, the catheter may be clamped and remain in for the 2-hour dwell time, or it may be removed, per the discretion of the investigator. Subjects will be instructed to hold the study drug in the bladder for 2 hours. During this time, subjects will be required to the best of their ability, to position themselves upright (standing or sitting), prone, supine, and in the left and right lateral decubitus positions for at least 15 minutes each, in any order. After 2 hours, the bladder will be drained and the catheter removed (if the catheter remained in place) or the subject will void to empty their bladder. The subject must remain at the clinic for the entire 2 hour dwell duration.
	

An appropriate local anesthetic and sterile lubricant may be used at the time of catheterization. In addition, an antibiotic may be given at the discretion of the Investigator.
	

Study Procedures: At each dosing visit, pre-dose and post-dose, vital sign measurements and adverse event assessments will be conducted. At the Screening cystoscopic assessment, visual mapping and recording of the position of tumors in the bladder must be performed, including quantification of the overall area of the bladder affected. Directed biopsies will be performed prior to the first dose to histologically confirm non-muscle invasive bladder cancer. Urine cytology will be performed prior to the last dose in the Induction Phase, and cystoscopy will be performed at the end of the Induction Phase. Cystoscopy and cytology will also be assessed every 13 weeks (3 months) during the Maintenance Phase. At each cystoscopic evaluation while the subject is on-study, directed biopsies should be taken from all areas of apparent disease or suspicious for disease, including any area of inflammation. When positive or suspicious cytology is observed in the case of negative cystoscopy, random bladder biopsies will be obtained from the locations of disease identified at Screening (i.e., by screening biopsies and the screening bladder mapping) and from other areas of the bladder so that all the following areas of the
	

bladder have been biopsied: the dome, the posterior wall, the left and right lateral walls, the trigone and the bladder neck, and in males, the prostatic urethra. Blood will be drawn at Baseline, during week 12 and after approximately 6 months of therapy for determination of plasma anti-Vicinium antibodies. Blood will be drawn on Day 1 pre-dose and at the end of the 2-hour dwell time, and at the end of the 2-hour dwell time in Week 6 (12th treatment) and Week 12 for the determination of Vicinium plasma levels. Periodic clinical lab tests and pregnancy tests (in females) will be performed.

Additional study procedures will include triplicate ECGs for QTc analysis at completion of the Induction Phase and EpCAM determination by immunohistochemistry on all positive biopsies.

**Post-Treatment Evaluation:** Subjects will return for Post-Treatment evaluations between 30 and 37 days after their last dose of study treatment. Post-treatment procedures include cystoscopy, directed biopsy and urine cytology (if the subject has not discontinued protocol therapy due to disease recurrence or progression and if these evaluations have not been performed in the prior 8 weeks), as well as safety assessments of vital signs, triplicate ECG, physical examination, clinical laboratory analyses, and adverse events and concomitant medications assessments. If a cystoscopy is required, it should be performed as soon as possible on or after Day 30 post-treatment.

**Number of subjects (planned):** Approximately 134 subjects.  $\geq 77$  subjects will enroll in Cohort 1. Up to 57 subjects will enroll in Cohort 2 and Cohort 3 combined.

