### **10.6 Post-Treatment Evaluation**

Subjects will return to the clinic site for a Post-Treatment evaluation 30 – 37 days after their last dose of study treatment.

The following assessments will be performed at that time

- Targeted physical examination (including weight) ([Section 16.3](#))

- Triplicate ECG obtained within 30 minutes of each other at least 3 minutes apart
- Vital signs
- Concomitant medications
- Adverse events, including SAEs
- Collection of clinical laboratory samples: blood samples for hematology and chemistry, urine samples for urinalysis
- Anti-Vicinium antibodies
- Blood or urine pregnancy test (WOCBP)
- The following are to be done if the subject has not discontinued treatment due to documented disease recurrence, progression and if they have not been performed within the past 8 weeks
  - Cystoscopy
  - Biopsy (directed). EpCAM determination by immunohistochemistry will be obtained on all positive biopsies.
  - Urine cytology

As described in **Section 15**, additional follow-up will occur for subjects with ongoing clinically significant AEs (e.g., those leading to study drug discontinuation) or SAEs assessed as related to study drug.

Subjects without a treatment failure (see **Section 14.2**) will continue to undergo evaluations for disease status (urine cytology, cystoscopy, directed biopsies) every 13 weeks until the sooner of a treatment failure or the determination of the 18-month event free survival analysis. Survival data also will be collected on subjects every 13 weeks. Once all subjects are no longer receiving study treatment and the 18-month event-free survival for the study is determined, the study will close and subjects will then be followed by their physician according to standard of care.

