### **11.3 Study Withdrawal Criteria**

Subjects are free to withdraw from treatment or from any further participation in the study (i.e., withdraw consent) at any time and without prejudice to further treatment. The Investigator should discuss with the subject if they want to withdraw from further treatment only (i.e., additional data will be collected) or from all further study participation at which time no data will be collected for the subject. The investigator must withdraw a subject from all further study participation if that subject withdraws consent. No additional evaluations will be done or data collected for subjects who withdraw consent. All subjects withdrawing from further study treatment should have Post-Treatment evaluation 30 – 37 days after the last dose of study treatment and receive follow up disease evaluation (every 3 months ([Section 10.6](#)) and until a protocol-defined event as well as be contacted for data secondary endpoint (PFS, OS). The reasons and details relevant to subject withdrawal must be recorded in the case report form (CRF). The Investigator must notify the Medical Monitor if a subject is withdrawn from the study.

Subjects must be withdrawn from study drug for any of the following reasons:

- Withdrawal of informed consent
- Pregnancy ([Section 12.5](#))
- Treatment failure ([Section 14.2](#))
- Documented extravesical (i.e., upper or lower tract) urothelial carcinoma
- Development of a second malignancy that requires systemic therapy
- Cystectomy
- Unacceptable toxicity
- Persistent non-compliance with the protocol requirements
- Treating physician / study Investigator concludes that it would be in the subject's best interest
- Intercurrent illness that, in the judgment of the Investigator, may affect assessments of clinical status to a significant degree, and that requires discontinuation of study drug.
- Sponsor terminates the study.

Subjects may be considered withdrawn if they fail to return for visits, or become lost to follow-up for any other reason. Every attempt should be made to re-establish contact for subjects who are lost to follow-up (i.e., those subjects whose status is unclear because they fail to appear for study visits without stating an intention to withdraw). The Investigator should undertake appropriate due diligence and document steps taken to contact the subject (e.g., dates of telephone calls, registered letters).

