Subjects' disease status will be evaluated based on cystoscopy (and biopsies if indicated) and urine cytology at the end the Induction Phase (week 13) and every 13 weeks during the Maintenance Phase (i.e., Week 26, Week 39, Week 52, Week 65, Week 78, Week 91, Week 104) regardless of dosing interruptions or delays. For subjects who discontinue treatment for reasons other than disease progression ([Section 14.2](#)), cystectomy or death, the every 13-week disease evaluation should continue for the determination of secondary endpoints e.g., event-free survival, progression-free survival. Every effort should be made to stay on this evaluation schedule, however, a window of one week before and up to 2 weeks after these time points is permitted (e.g., the Week 26 cystoscopy and urine for cytology may be performed from week 25 to week 28, but as close to Week 26 as possible). The complete evaluation to determine disease status may require a repeat cytology and repeat cystoscopy with biopsies (See [Table 7](#)) and should be completed as soon as possible following the every 13-week timepoint. On cystoscopy, any areas suspicious for disease must be biopsied. In situations where there are no suspicious lesions on cystoscopy but a positive or suspicious result on urine cytology, random bladder biopsies will be obtained from the locations of disease identified at Screening (i.e., by screening biopsies and the screening bladder mapping) and from other areas of the bladder so that all the following areas of the bladder have been biopsied: the dome, the posterior wall, the left and right lateral walls, the trigone and the bladder neck, and in males, the prostatic urethra. A second urine cytology will also be required at the time of evaluation if the result of the first urine cytology is suspicious for urothelial carcinoma. The use of other diagnostic evaluations (e.g. urine FISH) or the performance of additional urine cytology, cystoscopies, and/or biopsies not mandated by the protocol may be performed when clinically indicated per the investigator's clinical judgment or standard of care. Results of urine FISH will not be considered in the response evaluation but may be used by the investigator to guide additional (non-protocol mandated) evaluations.

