1.4. LIST OF ABBREVIATIONS

Abbreviation	
AE	adverse event
BCG	bacillus Calmette-Guérin
BIW	twice weekly
CFU	colony forming units
CIS	carcinoma in situ
CRF	case report form
CT	computerized tomography
CTCAE	Common Terminology Criteria for Adverse Events
DSMB	data safety monitoring board
ECG	electrocardiogram
FDA	Food and Drug Administration
EFS	event-free survival
EpCAM	epithelial cell adhesion molecule
MedDRA	Medical Dictionary for Regulatory Activities
mITT	modified intent-to-treat
MRI	magnetic resonance imaging
NCI	National Cancer Institute
NMIBC	non-muscle invasive bladder cancer
OS	overall survival
PFS	progression-free survival
PK	pharmacokinetics
QTc	corrected QT interval
QTcB	corrected QT interval - Bazett's correction
QTcF	corrected QT interval - Fridericia correction
SAE	serious adverse event
SD	standard deviation
SOC	system organ class
Ta	non-invasive papillary carcinoma
T1	tumor invades lamina propria
T2	tumor invades muscularis propria
TEAE	treatment-emergent adverse event
TPP	time to progression
TURBT	transurethral resection of bladder tumor(s)

2. **OBJECTIVES**

To assess the efficacy and tolerability of Vicinium when administered as a monotherapy intravesical instillation in subjects with non-muscle invasive bladder cancer - CIS, high-grade Ta or any grade T1 papillary disease or CIS plus papillary disease who failed previous treatment (i.e., not those who are intolerant) with BCG.

Primary endpoints:

Complete response rate at 3 months in subjects with CIS (with or without papillary disease) whose disease is refractory or relapsed in 6 months or less or relapsed from 6 months to 11 months following adequate BCG treatment.

Duration of response (DoR) will be estimated (Kaplan-Meier Estimate) for those subjects with CIS (with or without papillary disease) who experience a complete response.

Secondary endpoints:

- Complete response rate in subjects at 6, 9, 12, 15, 18, 21, and 24 months in subjects with CIS
- Event free survival (EFS) in all subjects
- Cystectomy-Free Days in all subjects
- Time to disease recurrence in papillary subjects
- Progression-free survival (PFS) in all subjects
- Overall survival (OS) in all subjects
- Safety and tolerability of Vicinium therapy in all subjects

Exploratory:

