5.2. EFFICACY ANALYSIS

5.2.1. Primary Efficacy Endpoint

The primary outcome measure is the complete response rate in subjects with refractory /relapsed CIS or CIS plus papillary disease (i.e., cohorts 1 and 2) following the initiation of Vicinium therapy.

Patients who discontinue or die before Month 3 will be included in the denominator of the primary analysis.

For the primary efficacy endpoint analysis, the following conventions will be utilized in determining treatment failure or complete response at a given visit.

1. Subjects that have centrally read pathology findings ('CIS', 'any-grade T1', 'high-grade Ta') or centrally read cytology results ('High Grade Urothelial Carcinoma') that indicate treatment failure for a given visit will be considered to have treatment failure.
2. Subjects who met a treatment failure criterion at a previous visit are treatment failures at all subsequent visits.
3. Subjects who have discontinued the study on or prior to the visit and have missing data that would be necessary to generate response are considered non-CRs.
4. Subjects who do not meet criterion 1-3 are complete responders.

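### The documents disagree on how long off-drug, failure-free CIS subjects are evaluated, and the SAP scores their unexamined late visits by default in a direction it leaves undefined

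*Protocol*

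**What the plan says.** **Time points reported.** The protocol synopsis lists "Complete response rate in subjects at 3, 6, 9, 12, 15, 18, 21, and 24 months in subjects with CIS", and Section 9.2 repeats the series. SAP Section 2 keeps the late visits: "Complete response rate in subjects at 6, 9, 12, 15, 18, 21, and 24 months in subjects with CIS". Months 21 and 24 are the Week 91 and Week 104 evaluations, which subjects still on drug undergo (Protocol 10.5).

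**End of evaluation for off-drug subjects without failure.**
- Protocol 10.6: evaluations run every 13 weeks "until the sooner of a treatment failure or the determination of the 18-month event free survival analysis".
- Protocol 11.3: evaluation continues every 3 months, with a cross-reference to 10.6, "and until a protocol-defined event as well as be contacted for data secondary endpoint (PFS, OS").
- Protocol 14: "the every 13-week disease evaluation should continue for the determination of secondary endpoints e.g., event-free survival, progression-free survival".
- Synopsis, Methodology: after the post-treatment visit, "additional subject data will be collected as needed for the evaluation of the Secondary Endpoints".

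**What the SAP says about off-drug data.** In SAP 3.3.7, the definitions of an event, of time to disease recurrence and of PFS state that disease assessments are not recorded once treatment is discontinued. Footnotes to the censoring tables limit this to discontinuation for an adverse event. The EFS definition in the same section censors at the last assessment and includes long-term follow-up in that. The visit windows in 3.3.8 and 3.3.9 run to Study Day 1501.

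**Scoring.** SAP 5.2.1 applies four rules in turn. Rule 3 makes a subject non-CR if data needed for response are missing and the subject has discontinued the study by that visit. Rule 4 is the remainder: "Subjects who do not meet criterion 1-3 are complete responders".

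**The concern.** An off-drug responder may have no examination at Month 21 or 24 because the protocol, on one reading, no longer asks for one, or because the result was not recorded. The stop in 10.6 belongs to a different endpoint, EFS at 18 months, and can fall before the last CR time point. Sites reading 10.6 and sites reading 11.3 or 14 could act differently.

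SAP 5.2.1 has no category for a visit at which no evaluation took place. The subject is called non-responder or responder according to a disposition field. The late CR rates would then depend partly on how a subject's status was recorded and not on an examination of the bladder.

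No planned analysis would show this. SAP 5.2.3 acknowledges that CR is presumed without evidence of failure. Its first sensitivity analysis, however, needs an abnormal cystoscopy at the visit and failure at the next one, so it cannot reach a visit with no examination. Its second concerns low-grade Ta only. SAP 3.3.4 imputes nothing else.

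**Working it through.** The plan gives no figure for this point, so there is none to reproduce. The check compares the text and then the calendar.

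**1. Level of the stop.** Protocol 10.6 continues: "Once all subjects are no longer receiving study treatment and the 18-month event-free survival for the study is determined, the study will close". The trigger is therefore one date for the whole study. Being off treatment and the EFS determination are listed as two separate conditions for closure, so they need not coincide.

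**2. Which default applies.** Protocol Section 10 says that subjects who meet criteria for stopping study drug are withdrawn from the study. That points to rule 3 (non-CR). Section 10.6 keeps evaluating the same subjects, and the study stays open until everyone is off drug. That points to rule 4 (CR). Neither document defines study discontinuation for this purpose.

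**3. When 18-month EFS is determined.** No document dates it. SAP 3.4 schedules analyses at 3, 6 and 12 months of follow-up and a final analysis after all subjects are off treatment. There are two cases.

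*Case A: at the final analysis.* The stop comes after the last on-drug subject has left treatment, which may be as late as Week 104. It removes a Month 21 or 24 visit only if the late enrollees all stopped drug early. The loss is near zero.

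*Case B: when the last subject reaches 18 months.* Assume uniform accrual over A months. A visit at month v falls after the stop for a share (v − 18 − lag)/A of subjects, where lag is the time from the last subject's Month 18 to the determination.

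| A (months, assumed) | Month 21, no lag: 3/A | Month 24, no lag: 6/A | Month 24, 3-month lag: 3/A |
|---|---|---|---|
| 12 | 25% | 50% | 25% |
| 24 | 12.5% | 25% | 12.5% |
| 36 | 8.3% | 16.7% | 8.3% |

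With a 3-month lag, no Month 21 visit is lost. The synopsis dates (August 2015 to August 2018) give 36 months. Less 24 months of treatment, that implies about 12 months of accrual, the row with the largest loss.

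**4. Number of subjects in Case B.** Assume 20 CIS subjects in CR at Month 18, of whom 10-40% are off drug without failure. The documents give neither figure.
- Month 24, low: 20 × 0.10 × 0.167 = 0.3. High: 20 × 0.40 × 0.50 = 4.
- Month 21, low: 20 × 0.10 × 0.083 = 0.2. High: 20 × 0.40 × 0.25 = 2.

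**5. Effect on the rate.** Take 77, the planned minimum for Cohort 1, as denominator. Four subjects are 4/77 = 5.2 percentage points, and 0.3 subjects is 0.4 points. As an example, suppose 12 subjects are documented CR at Month 24 and 4 are unexamined. Rule 3 for all four gives 12/77 = 15.6% (95% CI 8.3-25.6%). Rule 4 for all four gives 16/77 = 20.8% (12.4-31.5%). The SAP's pooled Cohort 1 and 2 denominator would be larger and the shift smaller.

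**6. The other source.** If assessments really are not recorded after treatment discontinuation, the defaults can decide every visit after drug stops, in Case A as well. The documents give no off-drug rate, so this part cannot be sized. Because it is not confined to late enrollees or to the last two visits, it is potentially larger than the 10.6 stop.

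**The case against.** The strongest reply is about timing. Protocol 17.7 plans no formal interim analysis, the SAP schedules nothing at 18 months, and EFS outputs appear only in the final-analysis list (SAP 12). The EFS power statement also assumes 24 months of follow-up. On that reading the 10.6 stop costs almost nothing. This stands as one of the two cases, but 10.6 does not say it, and it does not touch the SAP statement that off-drug assessments go unrecorded.

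A second reply is that 11.3 cites 10.6 and can be read together with it. That is possible. It does not resolve Section 14, the synopsis or the reported time points. Section 11.3 also names no week, so it cannot be taken to imply evaluation to Week 104.

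A third is that withdrawal under Section 10 leads to rule 3, which is conservative. That would settle the direction if 10.6 did not keep the same subjects under evaluation.

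Finally, Months 21 and 24 are secondary time points without a stated hypothesis test, and duration of response is already censored at the last assessment. Both are true, and they limit the consequence.

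Two stronger readings are tempting. A reader might infer that each subject's evaluation stops at his or her own 18 months, so that all off-drug responders are lost (20 × 10-40% = 2 to 8 of 20). The wording of 10.6 ties the stop to the study, so that figure is not supported. A reader might also infer that the late CR rates are inflated. Rule 4 would do that and rule 3 the opposite, and the documents do not choose between them.

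**Conclusion.** The concern holds as an internal conflict with an undefined scoring consequence. Protocol 10.6, 11.3 and 14, together with the SAP's own statements, do not give one end of disease evaluation for off-drug, failure-free CIS subjects. SAP 5.2.1 then classifies an unexamined visit by default, and rule 4 as written counts an unexamined subject as a complete responder unless study discontinuation is recorded.

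The 10.6 stop alone costs from near zero (Case A) to 8-25% of off-drug responders at Month 21 and 17-50% at Month 24 (Case B, no lag). The Case B figures at Month 24 amount to about 0.3 to 4 of 20 responders. They rest on assumed uniform accrual over 12 to 36 months, 20 Month-18 responders and 10-40% off drug, and a lag before the determination lowers them. Subjects on drug at Weeks 91 and 104 are not affected. The possible non-recording of off-drug assessments may matter more and cannot be quantified from the documents. The point should be corrected, but it does not show that the reported rates would be biased in a known direction.

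**What to change.** **Protocol.** Reconcile 10.6, 11.3 and 14 so that one stated end of disease evaluation for off-drug subjects without failure covers every CR time point reported. If the 18-month EFS determination is kept as a study milestone, say when it occurs.

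**SAP 3.3.7.** Reconcile the statements that off-drug assessments are not recorded with the adverse-event footnotes and the long-term follow-up provisions.

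**SAP 5.2.1.**
- Amend rule 4 so that a visit with no disease evaluation is not scored CR.
- State whether an off-drug subject still under evaluation counts as having discontinued the study.
- Report the number of unexamined subjects at each visit.

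**SAP 5.2.3.** Add a sensitivity analysis counting all unexamined visits as non-CR. This keeps the by-visit Clopper-Pearson series intact. Kaplan-Meier estimates at only the last two visits would mix estimators and assume that off-drug responders fail at the same rate as the others.

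**Cost.** The late CR rate may be slightly less favourable, and there is a little more analysis work. The SAP scoring changes need no new data. The protocol alignment means at most two further evaluations, Weeks 91 and 104, for the few subjects whom the 10.6 stop would have cut off.
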